Study Design

This project will have several components, which we anticipate will unfold over the course of 5 years. The first step of the process will be training research and clinical staff; practicum students, psychology residents, and staff clinicians at CAMH on administering the Modular Approach to Therapy for Children with Anxiety, Depression, Trauma, and Conduct Problems (MATCH-ADTC) treatment. The study investigators will be primarily involved in training clinical staff on MATCH-ADTC treatment. They will not be directly involved in administering care, but they will be responsible for supervising practicum students and residents administering care. These students are clinical trainees in a doctoral program for clinical psychology, supervised by registered psychologists at CAMH (e.g., [name], [name]). These students have previously completed coursework and training in therapeutic methods. When matching clients to students, we will consider the expected length of treatment in relation to the length of their practicum or residency. Most practicums and residencies range from 9 months to 12 months, which will provide ample time to complete most courses of treatment. In the case that a student is unable to complete a course of treatment for a client, we will ensure continuity of care as is standard within our clinical services. There would be a plan for a warm transfer, where another trainee or clinician would continue treatment.

Children and their parent(s)/caregiver(s) will be recruited on an ongoing basis from two outpatient children's mental health clinics (CAMH and University of Guelph). Senior research staff will screen families, enroll them in the study, and conduct pre-treatment assessments. After enrolment and collection of initial measures, participants will be randomly assigned to the intervention arm or the waitlist control arm. We anticipate that the duration of both MATCH-ADTC treatment and the waitlist will range between 4 – 6 months, which is similar to the usual wait times for services at both clinics.

During this period, participants in both arms will complete brief weekly measures, which consist of very brief symptom scales. Participants will be required to complete quarterly assessments (approximately 3 months following their initial assessment), which will consist of symptom scales, medication tracking, clinical interviews, experimental tasks and physiological measures.

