Parent(s)/caregiver(s) invited to participate in this research study will be asked to provide informed consent before the initial assessment. They will be provided a copy of the informed consent form via REDCap, and trained senior lab members will review the consent form with them. Upon clicking the link, participants will review the landing page and continue on to the text. The contents of the informed consent form will be displayed according to the submitted consent form, minus the signature/attestation page. The lab member will explain the purpose of the study, treatment intervention, risks, benefits, expected duration, participants' responsibilities, compensation, confidentiality, privacy, and that participation is voluntary. Due to clinician availability, participants randomized to MATCH-ADTC will not receive treatment immediately, and will be added to a waitlist that will be separately maintained from the clinic's waitlist. Participants will be informed of the estimated duration of the waitlist for both MATCH-ADTC and usual care prior to enrollment in the study. Additionally, they will be informed of the benefits and drawbacks of both MATCH-ADTC and usual care waitlist. The benefits of MATCH-ADTC are that they will be provided with individualized, flexible and tailored treatment. However, MATCH-ADTC is not offered in a group format, which can be beneficial for children and parent(s)/caregiver(s). Parent's and children who choose not to participate in the study or who are waiting for usual care (control arm) will be informed of the potential benefits of usual care and that the treatments are typically evidence-based, well-established and structured, and can be offered in group or individual formats. Group treatment can be beneficial for children with peer difficulties and can benefit parents by having the support of other parent(s)/caregiver(s) with similar experiences. If at any point during the study, a participant decides to withdraw from the study, additional research visits will not be scheduled, and measures will not be sent. If a participant decides to withdraw after having already begun MATCH-ADTC treatment or treatment as usual, they will continue to receive treatment. The participant will be given time to ask any questions and review the consent form on their own.

Parent(s)/caregiver(s) will be asked to provide consent for themselves and their child:

- Consent to participation in the study

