Parents and children can opt to have their weekly measures sent to them via email or texted to their mobile devices via Twilio. Twilio is a widely used third-party SMS provider integrated with the REDCap platform. Once the participant clicks on a link to the survey, they will fill out the REDCap survey on their mobile device. Participants' SMS records do not stay on Twilio's logs, but are removed shortly after being completed, for security and privacy purposes.

There will be several in-person study visits throughout the course of this study. All in-person visits are dependent on COVID-19 protocols as determined by provincial and CAMH guidelines. All visitors to CAMH (during pandemic periods) are required to show proof of vaccination, complete a COVID screening and masks are worn at all times. If the situation arises in which in-person visits became unfeasible, we would adjust our assessment procedures as necessary.

The initial pre-randomization study visit will be completed shortly after enrollment in the study and prior to starting MATCH-ADTC treatment (for those assigned to that condition). Quarterly study visits will be conducted at 3-month intervals while the participant is in the waitlist control arm or in MATCH-ADTC treatment. The post-study visit, for those in the waitlist control arm will be conducted 4-6 months after the initial study visit or prior to them being picked up off the waitlist to be seen for usual care (i.e., whichever is sooner). A participant in the treatment condition will be seen for a post-assessment after completion of MATCH-ADTC treatment (i.e., usually about 3-6 months).

If a participant becomes uncomfortable or distressed during a study visit, they will be able to take breaks as needed or reschedule the study visit to a later date. If a participant becomes significantly distressed during an assessment, they will be provided with additional resources for support (e.g. Kids Help Phone, What's Up Walk-In Clinics). A clinician will be available in an on-call capacity to conduct risk assessments and provide support (e.g. de-escalation) for participants.

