Two randomized effectiveness trials have demonstrated MATCH's effectiveness against usual care and standard treatment protocols (Cohen's d s from .47 to .55)⁴³⁻⁴⁴. MATCH draws from various domains of evidence-based treatment and consists of 33 treatment modules. There are several core module sequences for problem areas such as depression, anxiety, trauma, or disruptive behaviour and a clinician can utilize these sequences based on the primary concern for the individual. MATCH treatment usually ranges from 4 – 6 months, but the duration is flexible and dependent on the individual's needs. If an individual reports additional stressors or comorbid conditions, the clinician can modify the sequence of the modules to address these comorbidities. For example, if a child has been referred for the treatment of conduct problems, the clinician may utilize behavioural parent training, rewards, and time outs. If the child were to further report depressive symptoms, the clinician could incorporate modules from the depression pathway, such as problem solving and cognitive restructuring. MATCH treatment is flexible and can be tailored for each individual, so it is highly effective⁴⁵.

Clinicians administering MATCH-ADTC treatment will be asked to complete a Therapist Background Questionnaire⁴⁶, which asks about their training, educational background, and experience with child psychotherapy. They will have regular team meetings with the principal investigators ([name], [name], [name]) to discuss the implementation of the MATCH treatment program. These consultation meetings – which will not entail clinical supervision – are to support the implementation of MATCH with high fidelity. Brief consultation notes will be documented. All information shared at these meetings will be de-identified and personal health information will only be discussed on an as needed basis (e.g. age, sex, mental health concerns). To establish treatment alliance, adherence, and fidelity, therapy sessions will be audio recorded. A randomly selected 20% of the sessions will be coded for fidelity using the Therapist Integrity in Evidence Based Interventions and Therapy Process Observational Coding System – Alliance Scale⁴⁷. Clinicians will complete weekly session notes and fidelity checks, and at discharge of each MATCH-ADTC client, clinicians will complete the *Therapist Satisfaction Index*⁴⁸.

Control Group

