Previous studies involving randomized waitlist controlled studies have established that MATCH-ADTC treatment is more effective than usual care. The justification of the control arm in this study is to allow us to evaluate the changes in biobehavioural regulation as a consequence of MATCH-ADTC treatment. The waitlist control exists to support our hypothesis that changes in emotion regulation are not merely due to the passage of time or normal emotional/psychological development in children.

The control arm of this project will consist of a no-treatment, waitlisted group. Participants in the waitlist condition will remain on the waitlist for standard usual care, and the estimated wait time is approximately 4-9 months. While in the waitlist control arm, participants are required to complete 75% of the weekly measures and attend both the quarterly (3-month) and the post-test study visit. If participants decide not to continue with the study, or they are lost to follow-up, they will be considered a drop-out in the Big Feelings Study, but their referral will remain open for usual care and they will remain on the clinic waitlist. Upon completion of the post-assessment, participants in the waitlist condition will be offered a bridging treatment (usually MATCH-ADTC treatment) until their usual care standard treatment spot becomes available, at which point they can decide whether they would like to continue with the bridging treatment or move to the standard care. Therefore, participants assigned to the control arm will also receive high quality, evidence-based treatment.

Compensation

Children and their parent(s)/caregiver(s) will be compensated for their participation. They will be provided with gift cards at each study visit and for completion of the weekly surveys. If participants are only able to complete the questionnaires, they still receive a portion of honorarium (see table, where the amount for “questionnaires” indicate how much participants can receive as honorarium for partial completion).

	Pre-Test Visit	Weekly Surveys	Quarterly Visit(s)	Post-Test Visit	
Parent	\$30 questionnaires only \$40 both questionnaires and in person visits	\$2 per survey \$5 bonus for every 5 completed	\$30 questionnaires only \$40 both questionnaires and in person visits	\$30 questionnaires only \$60 both questionnaires and in person visits	

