Preliminary analyses will test for significant differences in demographic factors between the MATCH and waitlist groups; significant factors will be covaried in our models. In the unlikely event that medication discrepancies are discovered between the two treatment groups, we will equate the groups by imposing propensity scores-based weighting in the analysis. An exploratory factor analysis (EFA) will examine whether the emotion regulation variables load onto a broad latent construct. Variables that do not load on the same factor will be examined independently within our mediation models. Latent Growth Curve (LGC) mediation modeling, which will account for the nested structure of the data as well as potentially unequally spaced time points, will test whether improvements in emotion regulation mediate improvements in symptoms as a result of MATCH treatment. We will conduct two types of mediation analyses corresponding to our operationalization of treatment response – pre-post change and trajectory of change. First, emotion regulation (latent biobehavioural regulation factor(s) from the EFA) will be modeled as a latent change from baseline to the 3-month quarterly assessment, and symptom change (CBCL/YSR internalizing and externalizing scores) will be modeled as a latent change from baseline to the post assessment. Our predictor will be specified as MATCH vs. Waitlist to ensure we can derive conclusions about the impact of MATCH on emotion regulation and symptoms. To test the mediated effect, we will apply the recommended bootstrap-based product of coefficients, which will yield bias-corrected 95% CIs based on the recommended asymmetric CI method. Second, to understand trajectories of change during MATCH treatment, we will apply LGC modeling to examine latent slopes of change in emotion regulation (weekly CADS) and symptoms (weekly BFS) and explore the temporal relations between the two trajectories. This will allow us to understand the temporal order and bi-directionality of changes in regulation and symptoms. In both modeling approaches, we will co-vary child age, gender/sex, medication use, puberty status, ethnicity, and treatment fidelity. We will apply an intent-to-treat approach and full information maximum likelihood estimation to account for potential bias caused by missing data.

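### The post visit runs from the initial visit in the waitlist arm but from treatment completion, after a wait of unstated length, in the MATCH arm, so the contrast at post can mix treatment with elapsed time

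*Protocol*

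**What the plan says.** Baseline measures are collected before randomisation (Study Design; Data Collection). After that the two arms follow different clocks.

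- **Waitlist arm (Data Collection):** "The post-study visit, for those in the waitlist control arm will be conducted 4-6 months after the initial study visit". The same sentence lets the visit come earlier for a child about to leave the waitlist, taking whichever date falls first. Six months is therefore the latest planned time.
- **MATCH arm (Data Collection):** "A participant in the treatment condition will be seen for a post-assessment after completion of MATCH-ADTC treatment (i.e., usually about 3-6 months"). No window from the initial visit or from randomisation is given.
- **Wait before MATCH (Consent and Assent):** "participants randomized to MATCH-ADTC will not receive treatment immediately, and will be added to a waitlist" kept apart from the clinic's own. Clinical Records also treats waiting for MATCH as a status distinct from being in treatment. Families are told an estimated wait, but the text available gives no figure.

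The stated durations do not agree. Study Design says "We anticipate that the duration of both MATCH-ADTC treatment and the waitlist will range between 4 – 6 months". MATCH Treatment says "MATCH treatment usually ranges from 4 – 6 months, but the duration is flexible". Data Collection gives about 3-6 months for MATCH. Control Group says of the waitlist that "the estimated wait time is approximately 4-9 months".

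The post visit feeds two comparisons. In Data Analysis, "symptom change (CBCL/YSR internalizing and externalizing scores) will be modeled as a latent change from baseline to the post assessment", with MATCH versus waitlist as the predictor. Study Design also plans to compare biobehavioural change between the arms at the post-assessment. Control Group says that the waitlist arm is there to rule out the passage of time and normal development as explanations for change in emotion regulation.

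**The concern.** A waitlist control removes the effect of time only if both arms are measured after the same amount of it. Here the interval from baseline to post is treatment length plus the MATCH wait in one arm, and at most 4-6 months in the other. Any untreated improvement or worsening over the extra months is then counted as an effect of MATCH.

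The exposed quantities are the total and direct effects of MATCH on CBCL/YSR change, and the post-visit comparison of biobehavioural change. The mediator is a separate question, because it is measured at the quarterly visit and the protocol gives that visit two clocks. Study Design puts it about 3 months after the initial assessment. Data Collection ties it to being in the waitlist arm or in MATCH treatment.

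Data collection matters more than analysis here. If nothing is measured during the MATCH wait, no later analysis plan can recover time-matched data for that period.

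**Working it through.** The protocol has no figure for this gap to reproduce, so the check builds it from the stated windows.

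**Inputs from the protocol.** Waitlist post visit at 4-6 months, midpoint 5 (Data Collection). MATCH treatment of 3-6 months, midpoint 4.5 (Data Collection), or 4-6 months, midpoint 5 (Study Design; MATCH Treatment). Analysed sample 168 (Sample Size), taken as 84 per arm.

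**Assumed, because not given.** MATCH wait W of 0-3 months. Untreated drift of 0.05 SD per month towards improvement, in SD units of the change analysed.

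**Formulas.**
- Gap = W + MATCH midpoint - 5. This is W with 4-6 months of treatment, and W - 0.5 with 3-6 months.
- Bias = drift x gap.
- SE = 2/√168 = 0.154.
- Rejection rate with no treatment effect = 1 - Φ(1.96 - bias/SE) + Φ(-1.96 - bias/SE).

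| W (months) | Gap, 3-6 / 4-6 months of treatment | Bias at 0.05 SD/month | Rejection rate |
|---|---|---|---|
| 0 | -0.5 / 0 | -0.025 / 0 SD | 5.3% / 5.0% |
| 1 | 0.5 / 1 | 0.025 / 0.05 SD | 5.3% / 6.2% |
| 2 | 1.5 / 2 | 0.075 / 0.10 SD | 7.7% / 9.9% |
| 3 | 2.5 / 3 | 0.125 / 0.15 SD | 12.8% / 16.3% |

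**Direction.** Positive values favour MATCH. If untreated children worsen by 0.05 SD per month, the W = 3 entry for 4-6 months of treatment becomes -0.15 SD.

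**If 3-6 months is counted from the initial visit.** The gap is 4.5 - 5 = -0.5 month, the same as the first entry in the W = 0 row: -0.025 SD, 5.3%.

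**Overlap of the windows.** With times spread evenly over the stated ranges, the share of MATCH post visits falling inside 4-6 months at W = 0, 1, 2 and 3 is 67, 67, 33 and 0% for 3-6 months of treatment. For 4-6 months of treatment it is 100, 50, 0 and 0%.

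**The quarterly visit.** On the Study Design clock, elapsed time is equal in the two arms, but treatment received by then is 3 - W months: 1 month at W = 2 and none at W = 3. On the Data Collection clock, read as starting with treatment, the MATCH visit falls at W + 3 months against 3 months in the waitlist arm, so the mediator change carries the gap W.

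**The case against.** The strongest counter-arguments are these.

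- **Equal durations are anticipated.** Study Design expects 4-6 months in both arms. That counts treatment and leaves out the wait before it, so the argument fails unless the wait is close to zero.
- **The model allows unequally spaced time points.** This helps trajectories with several measurements. In a two-point change each child has one interval. If its length follows the arm, the model cannot separate the two, and Data Analysis lists no elapsed-time covariate.
- **Weekly and quarterly data supply matched times.** Study Design has both arms giving weekly measures, and Data Analysis models the weekly slopes. This stands in part. It works only if collection covers the MATCH wait. The schedules refer to the intervention or waitlist period, or to being in the waitlist arm or in treatment, and none names that wait.
- **The wait may be documented elsewhere.** Families are told an estimate, so one exists, and consent pages are not part of the text available. This stands: the length is not shown here, which does not mean that nobody set it.
- **End of treatment versus wait is a recognised contrast.** This also stands. The design is not invalid; what the contrast can be said to show is limited.

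A reader might infer that about a third of null trials would look positive. The formula does give 34% for a 3-month wait and linear drift of 0.08 SD per month (3 x 0.08 = 0.24 SD). But that drift implies 8 x 0.08 = 0.64 SD of untreated improvement by month 8, more than the planned effect of 0.5. If drift instead slows, scaled to the same 0.40 SD at month 5, the month-8 excess is 0.40 x (ln 9/ln 6 - 1) = 0.09 SD on a log curve, or 0.06 SD on an exponential with a 3-month constant, and rejection is 6-9%. Nothing in the protocol supports using the extreme corner as the headline.

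**Conclusion.** The point holds. As written, time from baseline to post can differ by arm, and the contrast of CBCL/YSR change and the post-visit biobehavioural comparison then mix treatment with elapsed time. With 4-6 months of treatment the midpoint gap equals the wait; with 3-6 months it is half a month less.

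The size rests on an assumed wait and an assumed drift. At 0.05 SD per month it is 0.075-0.10 SD (8-10% false positives) for a 2-month wait, and 0.125-0.15 SD (about 13-16%) for a 3-month wait. It is negligible if the wait is near zero or if the 3-6 months run from the initial visit. The direction is not fixed either: a claim that the design favours MATCH goes beyond the text.

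Two opposite readings of the mediation test are tempting, and neither is supported without a condition. It is not simply safe, because on the Data Collection clock the mediator change is also taken at unequal times. It is not simply biased, because on the Study Design clock elapsed time is equal. There the cost of a long wait is that little treatment precedes the visit.

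This should be fixed. Confidence is medium, because the length of the MATCH wait decides whether the effect matters.

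**What to change.** 1. State that the quarterly visits and the weekly BFS and CADS run from the initial visit or randomisation in both arms, including the wait before MATCH. Reconcile Study Design, Consent and Assent, Data Collection, MATCH Treatment and Control Group on the MATCH wait, the treatment length, the waitlist length (4-6 or 4-9 months) and the quarterly clock.
2. Record the dates of randomisation, first session and every assessment, and report baseline-to-post time by arm.
3. Keep the baseline-to-post CBCL/YSR analysis, but describe it as end of treatment versus wait, not adjusted for elapsed time. Before attributing the difference to MATCH, add a supporting between-arm estimate at equal time since randomisation, from the weekly BFS and from CBCL/YSR where visits in the two arms overlap.

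**Cost.** Wording, date fields and some analysis; no extra post visit. If weekly surveys are not already planned during the MATCH wait, they add $2 per survey for each of parent and child, plus the $5 bonus for every 5 completed (Compensation).

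**Downside.** The contrast at a common month is smaller. If 0.5 SD builds linearly over 5 months of treatment, month 5 shows 0.5 x 3/5 = 0.30 SD after a 2-month wait and 0.5 x 2/5 = 0.20 SD after a 3-month wait. Power at a single visit with N = 168 is then 49% and 25%, against 90% for 0.5 SD. For that reason, making the common-month BFS contrast the main analysis, or moving the post visit, is a trade-off for the sponsor and not a required correction.

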Following the intervention or waitlist period, our team will conduct post- assessments. The post-assessments will allow us to analyze any changes in biobehavioural regulation and compare the differences between the intervention and control arms. Participants in the control arm will complete the post assessment approximately 4-6 months after their initial assessment, or prior to them being picked up off the waitlist for treatment in the clinic. . As screening and enrolment are ongoing, we will consistently clean data and engage in quality assurance procedures to ensure our methods are rigorous and meet scientific standards.

Participant Recruitment

Children will be recruited from the Child, Youth, and Emerging Adult Program (CYEAP) at CAMH and at the Maplewoods Centre for Family Therapy and Child Psychology at the University of Guelph.

Approximately 250 families (children aged 8 – 15, and their parent(s)/caregiver(s)), seeking psychotherapy for child anxiety, depression or disruptive behaviour will be recruited for this study. Families recruited from CAMH will have been referred to the Better Behaviours Service or Mood & Anxiety Clinic, or will be on the psychiatric assessment waitlist. Many families on the waitlist wait over a year for psychiatric evaluation, and many do not need or benefit from an assessment because they have been referred specifically for psychosocial treatment, and may already have a diagnosis and prescribed medication. To reduce the wait times for families and reduce the assessment burden, clinicians will screen families before their psychiatric assessment to identify children who may benefit from directly receiving psychosocial treatment without needing a psychiatric assessment first. These families will be contacted and asked to complete a short clinical screening (i.e. reason for referral) and approached to participate in research if the clinical team thinks the family would be a good fit. This process follows a similar procedure previously approved for use in our clinic (REB #018/2022).

Initial Research Contact

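### The MATCH post visit is triggered by completing treatment, so a child who stops early (read literally) or never starts (on any reading) has no scheduled post visit

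*Protocol*

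**What the plan says.** The Data Collection section gives the two arms different triggers for the post visit. For MATCH: "A participant in the treatment condition will be seen for a post-assessment after completion of MATCH-ADTC treatment". For controls: "The post-study visit, for those in the waitlist control arm will be conducted 4-6 months after the initial study visit", or before pick-up for usual care if that comes sooner. On the interim visits the same section says: "Quarterly study visits will be conducted at 3-month intervals while the participant is in the waitlist control arm or in MATCH-ADTC treatment".

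Three other places bear on this:

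- Study Design words the interim visit without a condition on treatment status: "Participants will be required to complete quarterly assessments (approximately 3 months following their initial assessment". Its post-visit sentence is general: "Following the intervention or waitlist period, our team will conduct post- assessments".
- Consent and Assent says that "participants randomized to MATCH-ADTC will not receive treatment immediately, and will be added to a waitlist", kept apart from the clinic's own list. It ends research visits when a family withdraws from the study. It does not address a family that stops therapy, or never starts it, and stays in the study.
- Data Analysis models symptom change from baseline to the post assessment and emotion-regulation change from baseline to the 3-month assessment. It then states: "We will apply an intent-to-treat approach and full information maximum likelihood estimation".

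**The concern.** An intent-to-treat contrast needs outcomes to be sought from every randomised child, whatever treatment the child received. In the control arm the trigger is mostly the calendar, which every child reaches. In the MATCH arm it is a treatment milestone, which some children will not reach. If staff follow the text, whether a MATCH child has a post outcome depends on how much treatment the child had.

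The interim rule may compound this. A child who has stopped, or who is still waiting for a therapist, is neither in the control arm nor in MATCH treatment. On the literal Data Collection wording the 3-month visit, which supplies the mediator, could be missed as well. A statistical analysis plan can choose how to model missing data, but it cannot recover visits that were never held. This is a separate matter from unequal elapsed time among children who do have a post visit.

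**Working it through.** The protocol gives no figure for stopping treatment, so there is none to reproduce. The check has two parts: which children have a scheduled visit, and what a gap could do to the estimate.

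**Which children have a visit**

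| Child's state | 3-month visit | Post visit |
|---|---|---|
| Control arm, in the study | Yes | Yes, by time from the initial visit or at pick-up if sooner |
| MATCH, completed | Yes, while in treatment | Yes |
| MATCH, stopped early, in the study | Yes under Study Design; not after stopping under Data Collection read literally | Only if completion means any end of treatment |
| MATCH, never started, in the study | Yes under Study Design; no under Data Collection read literally | None on either reading |
| Withdrawn from the study | No | No |

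The third and fourth rows are the gap. They also show that Study Design and Data Collection disagree on the 3-month visit.

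**What the gap could do to the total effect**

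Inputs:
- Effect in completers: d = 0.5, from Sample Size.
- Share q of MATCH children who stop or never start but stay in the study: not given; 0.1, 0.2 and 0.3 assumed.
- Share e of the benefit that they keep: not given; 0 and 0.5 assumed.

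All-randomised effect = 0.5 × (1 − q) + 0.5 × e × q

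- q = 0.1, e = 0: 0.45 + 0 = 0.45
- q = 0.2, e = 0: 0.40 + 0 = 0.40
- q = 0.3, e = 0: 0.35 + 0 = 0.35
- q = 0.2, e = 0.5: 0.40 + 0.05 = 0.45

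**What FIML would return (e = 0, stopping unrelated to baseline)**

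*Only baseline observed for stoppers.* FIML in effect predicts their outcome from completers with the same baseline, so the expected estimate is 0.50 at every q. A large simulation (400,000 children) gave 0.50, 0.49 and 0.50 for q = 0.1, 0.2 and 0.3. The completer contrast was also 0.50, 0.49 and 0.50.

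*A 3-month value observed for every child.* Assume that half the effect (0.25) has appeared by then and that the slope of post on 3-month value, given baseline, is 0.5. A stopper with no gain is 0.25 lower at 3 months, so the predicted gain is 0.5 − 0.5 × 0.25 = 0.375. The estimate is 0.5 × (1 − q) + 0.375 × q:

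- q = 0.1: 0.4500 + 0.0375 = 0.4875
- q = 0.2: 0.400 + 0.075 = 0.475
- q = 0.3: 0.3500 + 0.1125 = 0.4625

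The simulation gave 0.49, 0.47 and 0.46. At q = 0.2 the 3-month value therefore closes 0.50 − 0.475 = 0.025 of the 0.50 − 0.40 = 0.10 gap. It helps, but it does not replace the post visit.

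**The case against.** The best reply is that completion has been read too narrowly. MATCH has no fixed number of sessions; the MATCH Treatment section says "the duration is flexible and dependent on the individual's needs". Completion could then mean the end of whatever treatment was given, which fits the general post-visit sentence in Study Design. The CBCL description also has all parents completing it at pre- and post-test. This reading is reasonable for early stoppers, although the protocol never states it. It does not help a child who never starts, for whom no treatment period ends.

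Second, Study Design can be read as giving everyone a 3-month assessment. That stands as a reading, but it conflicts with the condition in Data Collection, and the 3-month visit is not the symptom endpoint. The 1-year follow-up mentioned elsewhere is not the endpoint either.

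Third, several stronger conclusions are tempting, and the documents do not support them:

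- A reader might infer that the analysis becomes a comparison among completers. It does not: FIML retains every randomised child. What would be limited to completers, on the literal reading, is the set of observed MATCH post outcomes.
- A reader might take 20% as the stopping rate and report a 25% overstatement (0.50/0.40 = 1.25). The 20% in Sample Size is study attrition, and families who leave the study would have no post visit under the fix either. The 25% also needs zero benefit in every stopper; with half the benefit it is 0.50/0.45 = 1.11, or 11%.
- A reader might infer that outcomes are lost only in the MATCH arm. The protocol expects attrition in both arms and describes waitlist drop-outs. Only the treatment-completion trigger is one-sided.
- A reader might carry these figures over to the mediated effect. They concern the total effect only. The second mediation analysis uses weekly measures and does not depend on the post visit.

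**Conclusion.** The point holds as a gap in visit scheduling. On any reading, a child randomised to MATCH who never starts has no post-visit trigger. On the literal reading, neither does one who stops early. The planned analysis would then rely on a missing-at-random assumption with little observed after stopping.

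The total MATCH effect on symptoms is likely overstated if stoppers gain less than completers. If many stop because they have already improved, the bias could shrink or reverse. Its size cannot be stated, because the protocol gives neither a stopping rate nor the benefit in stoppers. The illustrative all-randomised effects of 0.45 to 0.35 against 0.50 in completers rest on the assumed 10% to 30% with no gain. The FIML figures also rest on the assumed 3-month effect and slope. The bias in the mediated effect, the trial's main target, is not quantified.

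**What to change.** In Data Collection, state that every randomised child who has not withdrawn from the study is invited to the 3-month and post research visits, timed from the initial visit, whether or not MATCH was started, continued or completed. Add a calendar limit by which the post visit is held regardless, chosen with the MATCH waiting time in mind. Align the interim-visit and post-visit sentences in Study Design with this.

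The change concerns research visits only and leaves therapy decisions as they are. It costs some scheduling effort, and honoraria at the rates in the Compensation table, for families no longer in therapy. That table sets payments per visit; the protocol shows no visit budget, so it cannot be assumed that the added visits are already funded. The estimated effect may also come out smaller, because it would then describe all randomised children.
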